### 9.2.5.2 Reporting a Data Breach

#### Site Reporting Requirements

- Report to the Sponsor/UVA CC/GTcLC within 24 hours from the time the study team receives knowledge of the event.
- Report to your IRB of record in accordance with your IRB guidelines.

#### Sponsor/UVA CC/GTcLC Reporting Requirements

- Report to the UVA Corporate Compliance and Privacy Office as soon as possible and no later than 24 hours from the time the incident is identified. Report by telephone.
- Report to ITC if the breach involves electronic data. Report as soon as possible and no later than 24 hours from the time the incident is identified. Refer to the following for details: <http://security.virginia.edu/report-information-security-incident>.
- Report to UVA police if the breach includes such things as stolen computers. Report by telephone.

## 9.2.6 Protocol Violations or Deviations

### 9.2.6.1 Definition of a Protocol Violation/Deviation

A protocol deviation is defined as any change, deviation, or departure from the study design or procedures of a research project that is NOT approved by the institution's IRB prior to its initiation or implementation, OR deviation from standard operating procedures, Good Clinical Practices (GCPs), federal, state or local regulations. Protocol violations may or may not be under the control of the study team or UVa staff. These protocol violations may be major or minor violations.

### **9.2.6.2 Emergency Protocol Deviation/Violation**

When an emergency occurs that requires a violation of the protocol for a subject, this will be made only for that subject. A decision will be made as soon as possible to determine whether or not the subject (for whom the violation of, the protocol was affected) is to remain on study. This decision will be made by [name] [name] the IND holder. The subject's medical records will completely describe the violation of, the protocol and state the reasons thereof. In addition, the Investigator will notify the IRB/EC and the FDA as applicable in writing of such violation of, the protocol.

### **9.2.6.3 Non-Emergency Protocol Deviation/Violations**

Non-emergency minor violations of the protocol (i.e., deviations) will be permitted with approval of the PI.

It is the responsibility of the site investigator to use continuous vigilance to identify and report deviations.

### **9.2.6.4 Reporting of Protocol Deviations/Violations**

#### **Site Reporting Requirements**

- Report major deviations to the UVA CC/GTcLC within 4 calendar days from the time the study team receives knowledge of the event. All deviations must be addressed in study source documents. Refer to the Study Reference Manual for instructions on recording minor deviations.
- Report to your IRB of record in accordance with your IRB guidelines.

#### **Sponsor/UVA CC/GTcLC Reporting Requirements**

- Report to the UVA IRB-HSR major deviations within 7 calendar days from the time the study team received knowledge of the event. Report using the Protocol Deviation and Protocol Exception Reporting Form.
- Minor deviations do not need to be reported to the UVA IRB-HSR.

### **9.2.7 Method of Detecting AEs, SAEs, and Other Reportable Safety Events**

Care will be taken not to introduce bias when detecting AEs and/or SAEs and other reportable safety events. Open-ended and nonleading verbal questioning of the participant is the preferred method to inquire about AE occurrence.

### **9.2.8 Follow-up of AE, SAE, and Other Reportable Safety Event Information**

After the initial AE/SAE report, the investigator is required to proactively follow each participant at subsequent visits/contacts. All AEs, SAEs, and other reportable safety events including pregnancy and exposure during breastfeeding, events of clinical interest (ECIs), cancer, and overdose will be followed until resolution, stabilization, until the event is otherwise explained, or the participant is lost to follow-up.. In addition, the investigator will make every attempt to follow all nonserious AEs that occur in randomized participants for outcome. Further information on follow-up procedures is given in [section 11.5](#).

### **9.2.9 Sponsor Responsibility for Reporting Adverse Events**

All Adverse Events will be reported to regulatory authorities, IRB/IECs and investigators in accordance with all applicable country specific regulatory requirements, global laws and regulations.

## **9.3 Other Regulatory, Monitoring and Quality Assurance/Quality Control Considerations**

### **9.3.1 Foreign Sites**

All studies conducted under an IND will obtain a waiver of Institutional Review Board (IRB) requirements under 21CFRPart 56. The clinical parameters, data collection, data quality, and clinical trial conduct must adhere to U.S. regulations to be considered in the evaluation of a new drug application.

Reference to:

ICH guidance *E5 Ethnic Factors in the Acceptability of Foreign Clinical Data*:

<https://www.fda.gov/downloads/Drugs/Guidances/ucm073120.pdf>

Guidance for Industry and FDA staff: *FDA Acceptance of Foreign Clinical Studies Not Conducted Under an IND Frequently Asked Questions*.

<https://www.fda.gov/downloads/RegulatoryInformation/Guidances/UCM294729.pdf>

Guidance for Industry: *Investigator Responsibilities – Protecting the Rights, Safety, and Welfare of Study Subjects*.

<https://www.fda.gov/downloads/Drugs/GuidanceComplianceRegulatoryInformation/Guidances/UCM187772.pdf>

Office of Scientific Investigations.

<https://www.fda.gov/aboutfda/centersoffices/officeofmedicalproductsandtobacco/cder/ucm090085.htm>

### **9.3.2 Compliance & Monitoring**

The Global T-cell Lymphoma Consortium consists of a network of physicians whose expertise in T-cell Lymphoma whose mission is to advance the standards of care for patients with these complex diseases.

The consortium's three Principal Investigators represent three geographic sectors; Asia, North America, and Europe. Columbia University Medical Center (CUMC) will be the central reporting administration for the consortium. In this capacity the consortium will function similar to that of a clinical research organization (CRO).

Each global center will have a monitor at the site level who will follow the guidelines outlined in this document. A copy of monitoring reports will be made available to the Coordinating Center.

Each individual site will continue to follow their individual institution's guidelines for reporting purposes in addition to reporting these events to the centralized reporting administration of the consortium. The consortium central reporting administration will utilize the UVA Data Safety Monitoring Committee (DSMC) reporting templates for both serious adverse events and risk assessment. Reporting of SAEs will be in real time for each center using a 24 hour fax & email system. All necessary documentation will be sent including any pertinent labs and clinic /hospital notes. The necessary reporting to the UVA DSMC, IRB, and FDA will be the responsibility of the IND holder. When a protocol is conducted under an IND, the holder of that IND will follow their institutional guidelines in addition to reporting to the central reporting administration of the consortium. Each site within the Consortium will utilize their Institutional DSMB (DSMC or DMB) committee within each geographical sector. This is intended to satisfy the policies and recommendations of the U.S. Food and Drug Administration (FDA) and local ethics boards.

### **9.3.3 Study Monitoring**

Clinical site monitoring is conducted to ensure that the rights and well-being of trial participants are protected, that the reported trial data are accurate, complete, and verifiable, and that the conduct of the trial is in compliance with the currently approved protocol/amendment(s), with International Conference on Harmonisation Good Clinical Practice (ICH GCP), and with applicable regulatory requirement(s).

- The UVA Coordinating Center will implement ongoing monitoring activities for this study to ensure that Participating Institutions are complying with regulatory and protocol requirements, data quality, and subject safety. Monitoring will occur before the clinical phase of the protocol begins, continue during protocol performance and through study completion.
- Monitoring may be conducted either remotely or on-site. For remote visits, each institution will be required to provide redacted source documents for review or appropriate access to the EMR. The UVA CC/GTcLC will provide the Participating Institution with a follow-up letter following completion of the monitoring visit which should be maintained in the site regulatory files. The schedule for monitoring may be adjusted according to subject accrual and data quality. The Investigator will be notified in advance of each visit.
- Independent audits may be conducted by each institution according to institutional guidelines. Results of these audits may be requested by the UVA Coordinating Center.

Investigator responsibilities are set out in the ICH guideline for Good Clinical Practice (GCP) and in the US Code of Federal Regulations.

The University of Virginia Cancer Center Data and Safety Monitoring Committee (CC DSMC) will provide oversight of the conduct of this study. The CC DSMC will report to the UVA Protocol Review Committee (PRC).

The UVA Cancer Center DSMC will review the following:

- All adverse events
- Audit results
- Application of study designed stopping/decision rules
- Whether the study accrual pattern warrants continuation/action
- Protocol violations

Whenever a PAM audit (described in the next paragraph) is conducted, the results will be provided to the DSMC Chair for review. The UVA Cancer Center DSMC will meet every month for aggregate review of data. Tracking reports of the meetings are available to the PI for review. Issues deemed of immediate concern by the DSMC are brought to the attention of the sponsor (and if appropriate to the PRC and UVA IRB-HSR) and a formal response from the sponsor is requested. Per the UVA Cancer Center NIH approved institutional plan, this study will be audited (post-approval monitoring) approximately every 6 months. The audit may include direct access to source data/documents.

Any study conducted at UVA and under the purview of the University of Virginia HSR-IRB is subject to review of UVA documents. Studies are chosen for Post-approval Monitoring (PAM) either a) at random or b) requested by a study team member or any member of the IRB-HSR.

The purpose of Post-approval Monitoring audits is to ensure that documentation of clinical research studies is of the highest quality, verify protocol adherence, and ensure that all Federal and local rules concerning clinical research are being fulfilled. Post-approval monitoring is done by staff within the office of the Vice President for Research (VPR) in accordance with their Standard Operating Procedures. The conduct of an on-site review may include but is not limited to:

- requests for progress reports from investigators,
- examinations of research records, including signed informed consent documents, protocol modifications, and unexpected, serious, and/or related adverse experience reports,
- contacts with research subjects, or

- observation of the consent process and/or research procedures. Examples of when observation of the consent process could occur are:

- Full board IRB determines during review of a project that a conflict of interest exists such that the informed consent process should be observed by a neutral party;
- IRB is made aware of a complaint or concern with regard to the informed consent process; or

IRB determines as a result of the monitoring process that the consent process is insufficient and education/training is required for conduct of consent.

Investigators must enter study data onto CRFs or other data collection system. The Investigator will permit study-related audits by UVA Cancer Center or its representatives, IRB/EC review, and regulatory inspection(s) (e.g., FDA, EMEA, TPP), providing direct access to the facilities where the study took place, to source documents, to CRFs, and to all other study documents.

### **9.3.3.1 Quality Assurance and Quality Control**

Each clinical site will perform internal quality management of study conduct, data and biological specimen collection, documentation and completion according to institutional policies.]

Quality control (QC) procedures will be implemented beginning with the data entry system and data QC checks that will be run on the database will be generated. Any missing data or data anomalies will be communicated to the site(s) for clarification/resolution.

Following written Standard Operating Procedures (SOPs), the monitors will verify that the clinical trial is conducted and data are generated and biological specimens are collected, documented (recorded), and reported in compliance with the protocol, International Conference on Harmonisation Good Clinical Practice (ICH GCP), and applicable regulatory requirements (e.g., Good Laboratory Practices (GLP), Good Manufacturing Practices (GMP)).

The investigational site will provide direct access to all trial related sites, source data/documents, and reports for the purpose of monitoring and auditing by the sponsor, and inspection by local and regulatory authorities.

### **9.3.4 Study Records Retention**

Study documents should be retained for a minimum of 2 years after the last approval of a marketing application in an International Conference on Harmonisation (ICH) region and until there are no pending or contemplated marketing applications in an ICH region or until at least 2 years have elapsed since the formal discontinuation of clinical development of the study intervention. These documents should be retained for a longer period, however, if required by local regulations. No records will be destroyed without the written consent of the sponsor, if applicable. It is the responsibility of the sponsor to inform the investigator when these documents no longer need to be retained. Record retention will be in accord with drug 21 CFR 312.62 and HIPAA regulations.

## **10.0 STATISTICAL CONSIDERATIONS**

### **10.1 Study Design**

This is a Phase Ib study evaluating the safety and efficacy of pembrolizumab combined with pralatrexate (Arm A) or decitabine (Arm C) or decitabine and pralatrexate (Arm B) in patients with peripheral T-cell lymphoma (PTCL) and cutaneous T-cell lymphoma (CTCL). In all arms, toxicity will be assessed according to the NCI Common Toxicity Criteria for Adverse Events (CTCAE), version 5.0. Dose-limiting toxicity (DLT) is a binary outcome (yes/no) and will be determined by adverse events occurring during the first cycle of treatment (see Section 5.3 for DLT definition). In all arms, the maximum tolerated dose (MTD) is defined as the dose combination with a DLT rate closest to the target DLT rate of 25%. The study will accrue participants in cohorts of size 1 in all arms. After accrual of a participant to an arm, the accumulating DLT data will be used to update the model-based estimated DLT

probabilities for each dose level. These estimates will then be used to update the recommended dose level for the next participant accrued to that arm of the study.

Arms A and C:

The primary objectives of Arms A and C is to determine the MTD, defined by acceptable toxicity, of decitabine (Arm C) or pralatrexate (Arm A) (plus a fixed dose of pembrolizumab) from among the 3 study dose levels in the following tables, and to evaluate efficacy, as determined by overall response rate, at the estimated MTD.

Arm A		
Dose Level	Pralatrexate	Pembrolizumab*
Level 1 (start)	30 mg/m  day 1, 8, 15	200 mg day 1
Level -1	30 mg/m  day 1, 15	200 mg day 1
Level -2	20 mg/m  day 1, 15	200 mg day 1

Arm C		
Dose Level	Decitabine	Pembrolizumab*
Level 1 (start)	20 mg/m  day 1->5	200 mg day 8
Level -1	20 mg/m  day 1->3	200 mg day 8
Level -2	10 mg/m  day 1->3	200 mg day 8

Based on the accumulated data from the previous 5 subjects (1 observed DLT) accrued to Arm A, the first eligible subject in Arm A will be entered onto Level 1. Based upon the accumulated data from the previous 4 subjects (2 observed DLTs) accrued to Arm C, the first eligible subject in Arm C will be entered onto Level -1.

Arm B:

The primary objective of Arm B is to determine the MTD, defined by acceptable toxicity, of pembrolizumab combined with decitabine and pralatrexate from among the six study dose combinations in the following table, and to evaluate efficacy, as determined by overall response rate, at the estimated MTD. In a previous version of the protocol (dated 14 Dec 2022), fifteen dose combinations were considered for Part B. While the current protocol version reduces the number of dose combinations to six, we have maintained the original combination labels to maintain consistency with the original dose levels for each combination.

Combination designation			
Pralatrexate	20mg/m  1,8,15	Combination 6	Combination 8
	20mg/m  1,15	Combination 3	Combination 5
	15mg/m  1,15	Combination 1	Combination 2
		10mg/m  1-3	10mg/m  1-5
		Decitabine	

Based on the accumulated data from the first 4 subjects (1 observed DLT) accrued to Combination 8 in Arm B, the next eligible subject in Arm B will be entered onto Combination 8.

## 10.2 Dose allocation

### Arms A and C

Dose allocation in Arms A and C will be based upon a continual reassessment method (CRM), which uses a model for the probability of DLT and the accumulated DLT data at each dose level to sequentially allocate each new patient cohort. Toxicity assessment is based on the occurrence of DLTs, and the minimum follow-up for determination of escalation is one cycle of treatment. The DLT probabilities are modeled using a one-parameter working model  $R(d_i) = \Pr(\text{DLT at dose level } i) \approx \alpha_i^{\exp(a)}$ , where  $\alpha_i$  is the skeleton of the working model. The skeleton values are pre-specified constants and were chosen according to the algorithm of Lee and Cheung, which yields a working model that results in well-performing operating characteristics in a broad range of scenarios. For this study, the skeleton values are  $\alpha_i = (0.08, 0.15, 0.25)$ . Based on the available DLT data  $D = \{(y_i, n_i); i = 1, \dots, 3\}$ , where where  $y_i$  is the number of DLT's and  $n_i$  is the number of subjects treated on study dose level  $i$ , the likelihood is given by  $L(a) \propto \prod_{i=1}^3 (\alpha_i^{\exp(a)})^{y_i} (1 - \alpha_i^{\exp(a)})^{n_i - y_i}$ .

After accrual of each patient into the trial, the DLT probability estimates,  $\tilde{R}(d_i)$ , are updated via  $\tilde{R}(d_i) = \alpha_i^{\exp(\tilde{a})}; \quad \tilde{a} = \arg \max L(a)$ .

These estimates are used to sequentially allocate patients to the dose indicated by the modeling to have the estimated DLT rate closest to 25%. The study will accrue participants in cohorts of size 1 and dose levels will not be skipped. The coherence principle will be used, where the next patient will not be treated at a dose level higher than the current dose level if the current patient experiences a DLT. Additionally, the next patient will not be treated at a dose level lower than the current dose level if the current patient does not experience a DLT. The study will sequentially repeat the estimation procedure after the enrollment and follow-up of each cohort. The allocation procedure will be repeated until sufficient information about the MTD has been obtained according to the stopping rules described below.

### Arm B

Dose combination allocation in Arm B will be conducted using a DLT-adapted partial order continual reassessment method (POCRM) for dose-finding with combinations of agents. The study will accrue eligible participants in cohorts of size 1 and will be based upon a modeling approach that uses (a) a selected set of five possible orderings for the DLT probabilities and (b) a skeleton for the DLT probabilities under each ordering. In drug combination studies, the toxicity relationship between some of the combinations being studied may be uncertain. If a combination involves increasing the dose of one agent while decreasing the dose of the other agent relative to another combination, then it may not be known which is more toxic. For example, combination 2 is an increase in the dose of decitabine and a decrease in the dose of pralatrexate relative to combination 3, which creates uncertainty in the ordering of DLT probabilities between combination 2 and combination 3. The specification of multiple possible orderings of DLT probabilities accounts for these types of uncertainty in the modeling approach.

Possible orderings of DLT probabilities
1) 1-2-3-5-6-8
2) 1-2-3-6-5-8
3) 1-3-2-5-6-8
4) 1-3-2-6-5-8
5) 1-3-6-2-5-8

Skeleton of DLT probabilities under each ordering**						
Combination labels						
Order	1	2	3	5	6	8
1	0.012	0.03	0.062	0.11	0.174	0.25
2	0.012	0.03	0.062	0.174	0.11	0.25
3	0.012	0.11	0.03	0.174	0.062	0.25
4	0.012	0.062	0.03	0.174	0.11	0.25
5	0.012	0.062	0.03	0.11	0.174	0.25

\*\*Skeleton values were chosen according to the algorithm of Lee and Cheung (*Clin Trials*, 2009)

Within each ordering, the CRM is fit to estimate DLT probabilities using that ordering's working model and the accumulated data. For each possible ordering,  $m = 1, \dots, 5$  in the table above, the DLT probabilities are modeled via a one-parameter power model  $R(d_i) = \Pr(\text{DLT at combination } i) \approx p_{mi}^{\exp(\theta_m)}$ , where the  $p_{mi}$  are the skeleton values for order  $m$  given in the table above. Uniform prior weights  $\tau(m) = 1/m$  are placed on each possible ordering so that each ordering/skeleton is considered equally likely a priori. After accrual of each patient into the trial, the parameter  $\theta_m$  is estimated for each ordering by maximum likelihood estimation where the likelihood is given by

$$L_m(\theta_m) = \prod_{i \in \{1, 2, 3, 5, 8\}} \left( p_{mi}^{\exp(\theta_m)} \right)^{y_i} \left( 1 - p_{mi}^{\exp(\theta_m)} \right)^{n_i - y_i},$$

$y_i$  = the number of DLTs, and  $n_i$  = the number of treated patients in combination  $i$ . The ordering  $h$  with the largest likelihood is chosen and, within this ordering, DLT probability estimates are updated for each combination. If there is a tie between the likelihood values of two or more orderings, then the selected ordering  $h$  is randomly chosen from among the tied orderings. After accrual of each patient cohort into the trial, the DLT probability estimates,  $\tilde{R}(d_i)$ , are updated via

$$\tilde{R}(d_i) = p_{hi}^{\exp(\tilde{\theta}_h)}; \quad \tilde{\theta}_h = \arg \max L_h(\theta_h).$$

The DLT probability estimates are used to sequentially allocate participants according to the following rules:

1. If the most recent participant accrued to the study **does not** experience a DLT, then the recommended combination for the next participant will be the combination indicated by the model to have an estimated DLT rate closest to 25%. Escalation of both agents simultaneously or escalation of more than one dose level of either agent is not allowed.
2. If the most recent participant accrued to the study **does** experience a DLT:
  - a. If the DLT is mucositis or thrombocytopenia or mucositis plus neutropenia and/or thrombocytopenia, then the recommended combination for the next participant will be restricted to either the current combination administered to the most recent participant or to de-escalation of one dose level of Pralatrexate, based on which combination has an estimated DLT rate closest to 25%.
  - b. If the DLT is neutropenia or neutropenia and thrombocytopenia, then the recommended combination for the next participant will be restricted to either the current combination administered to the most recent participant or to de-escalation of one dose level of Decitabine, based on which combination has an estimated DLT rate closest to 25%

The study will sequentially repeat the estimation procedure after the enrollment and follow-up of each cohort. The allocation procedure will be repeated until sufficient information about the MTD has been obtained according to the stopping rules described below.

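### The printed Arm B likelihood omits Combination 6, so DLTs there would never update the dose-finding model

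*Protocol*

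**What the plan says.** Section 10.1 sets Arm B to find the MTD "from among the six study dose combinations in the following table"; they are labelled 1, 2, 3, 5, 6 and 8. Section 10.2 places Combination 6 in all five orderings and gives it a skeleton value in every row. It says that within each ordering "the CRM is fit to estimate DLT probabilities using that ordering's working model and the accumulated data", and that the parameter "is estimated for each ordering by maximum likelihood estimation where the likelihood is given by" the formula that follows. That formula multiplies over i in {1, 2, 3, 5, 8}.

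The ordering "with the largest likelihood is chosen and, within this ordering, DLT probability estimates are updated for each combination". If orderings tie, "the selected ordering $h$ is randomly chosen from among the tied orderings".

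Accrual continues from a stated position: "Based on the accumulated data from the first 4 subjects (1 observed DLT) accrued to Combination 8 in Arm B", the next participant is assigned to Combination 8. Section 10.3 stops the arm when the recommended combination already has 7 participants and declares that combination the MTD. The DLT-count safety bound applies to Combination 1 only.

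**The concern.** The index set contradicts the six-combination design, the orderings, the skeleton table and the statement that the accumulated data are used. Nothing in the protocol gives a reason to leave Combination 6 out, and section 10.5 simulates it and sometimes selects it.

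Combination 6 is easy to reach. It is one decitabine step below Combination 8, where the arm now stands, and rule 2b of section 10.2 offers that step after a neutropenia DLT. If the formula is coded as printed, participants treated at Combination 6 contribute nothing to the model that assigns the next participant and names the MTD. The arm could fill Combination 6 to seven participants and declare it the MTD without using their DLT outcomes.

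**Working it through.** **Inputs.** All are from Protocol 10.1–10.3 and 10.5: the power model p^exp(θ), the five printed skeleton rows, the 25% target, 1 DLT in 4 at Combination 8, rules 1, 2a and 2b, the stop at 7 on the recommended combination, the maximum of 30, and the bounds at Combination 1. The skeleton at Combination 8 is 0.25 in every row. At Combination 6 it is 0.174 (rows 1 and 5), 0.11 (rows 2 and 4) or 0.062 (row 3).

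**Step 1: a result that needs no simulation.** Suppose the fifth participant has a neutropenia DLT, so the data are 2/5 at Combination 8.

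- exp(θ) = ln 0.4 / ln 0.25 = 0.661, which puts Combination 8 at 0.40.
- Combination 6 is 0.174^0.661 = 0.315, 0.11^0.661 = 0.232 or 0.062^0.661 = 0.159. Distances from 0.25 are 0.065, 0.018 and 0.091, all smaller than the 0.15 for Combination 8. Rule 2b therefore sends the next participant to Combination 6 under any ordering.
- With data only at Combinations 8 and 6, the printed likelihood is the same for all five orderings, because only the 0.25 at Combination 8 enters. The ordering is drawn at random and these estimates never move.
- After a DLT at Combination 6, rule 2a compares staying with Combination 3, whose estimate is 0.062^0.661 = 0.159 (rows 1 and 2) or 0.03^0.661 = 0.098 (rows 3 to 5). Staying is closer to 0.25 in every row. Rule 2b has no lower decitabine level to offer, so the participant stays.
- Seven DLTs in seven participants would thus leave Combination 6 recommended, and section 10.3 would declare it the MTD.

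With Combination 6 in the product, one DLT there changes the fit. Orderings 1 and 5 tie as best, with exp(θ) = 0.4705. Combination 6 becomes 0.174^0.4705 = 0.44, and Combination 3 becomes 0.062^0.4705 = 0.27 or 0.03^0.4705 = 0.19. Rule 2a then moves down at once.

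**Step 2: simulation.** The design was simulated with 2,000 to 4,000 trials per setting, with and without Combination 6 in the likelihood. The Monte Carlo standard error at 3,000 trials is at most √(0.25/3000) = 0.9 points. Ties were broken at random, and every DLT was assumed to fall under rule 2a or rule 2b. The protocol does not state the mix of DLT types it simulated, so the share following rule 2a was varied.

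The protocol's own table was not reproduced exactly. With the rules as written and the full likelihood, Scenario 4 gives Combination 6 in 10–14% of trials against 5.00% printed, with average N 14.2–14.7 against 12.44. A narrower reading allows only staying or escalating one agent after a non-DLT. With 70% of DLTs following rule 2a, that reading gives about 5–6% and average N 12.2, but it misses Scenario 5 (Combination 2 about 28% against 18.90%).

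Percentage of trials declaring Combination 6 the MTD:

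| Scenario (true DLT rate at Combination 6) | Protocol table | Rules as written: all six | Rules as written: as printed | Narrower reading, 70% rule 2a: all six | Narrower reading, 70% rule 2a: as printed |
|---|---|---|---|---|---|
| 1 (0.15) | 1.36 | 2–3 | 32–34 | 1–2 | 10–11 |
| 4 (0.40) | 5.00 | 10–14 | 66–70 | 4–6 | 30–33 |
| 5 (0.47) | 6.12 | 6–9 | 67–72 | 6–7 | 43–44 |

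With the rules as written and the printed formula, the Scenario 4 figure stays at 66–70% for any rule 2a share from 0 to 1, and about 4.7–4.9 participants are treated at Combination 6, against 0.87 in the protocol. Under the narrower reading it depends on the share: about 56% at 25%, 46% at 50%, 33% at 70%, and 0% if every DLT follows rule 2a, since Combination 6 is then never reached.

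**The case against.** The strongest reply is that this is one missing symbol whose intended reading is plain. The text says the accumulated data are used, Combination 6 has a skeleton value in every row, and estimates are updated for each combination. The protocol's selection rates fit the full likelihood far better than the printed one, so the simulation code very likely included Combination 6. All Arm B data reported so far are at Combination 8, where the two likelihoods coincide, so the stated next assignment is right either way. The formula was also read from a PDF by a program, so the index set should be checked against the PDF.

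The size can be disputed too. The 67% belongs to Scenario 4 under a literal reading of rule 1, which does not reproduce the protocol's table. A reading closer to that table gives about a third, and the result depends on an unstated mix of DLT types. The bound at Combination 1 only is a design feature under either likelihood, and the DSMC meets monthly and reviews how the decision rules are applied (section 9.3.3).

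Most of this stands as context: it is probably a typographical slip, it has done no harm to the stated assignment, and its size if coded as printed is a range. It does not remove the error. The formula is the protocol's specification for dose assignment and MTD declaration, no other passage corrects it, and the protocol cannot show which version the live program follows. Committee oversight may catch an implausible recommendation, but it does not replace a correct likelihood.

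**Conclusion.** The concern holds. As printed, the Arm B likelihood excludes one of the six combinations under study, and DLTs at Combination 6 cannot change the model. Step 1 shows this exactly from the protocol's own numbers, without simulation.

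If coded as printed, Scenario 4 selects a combination with a true 40% DLT rate in about 67% of trials with the rules as written. Under the narrower reading with half to 70% of DLTs following rule 2a, the figure is about 30–46%. The protocol reports 5.00%. These figures rest on the printed skeletons, random tie-breaking and an assumed mix of DLT types. If the program already uses all six combinations, allocation is unaffected and the fault is that the protocol misstates its primary dose-finding model.

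**What to change.** In section 10.2, write the Arm B product over i in {1, 2, 3, 5, 6, 8}. Confirm, and record, that the live allocation program and the section 10.5 simulation code both use all six combinations. A quick test is to enter 2/5 DLTs at Combination 8 and 1/1 at Combination 6: a correct program returns about 0.44 for Combination 6, while one following the printed formula returns 0.16, 0.23 or 0.31. The cost is one symbol and a code check, and no dose or clinical rule changes. If the live program does omit Combination 6, any assignment made after a participant was treated there should be recomputed.
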